Amendment 4	01 Aug 2013	The primary purpose of this substantial amendment is for the dose for study participants already enrolled in RA0043 to be reduced (enrollment into RA0043 was suspended, effective 17 Jul 2013). An overall dose reduction for pediatric study participants of 50% of the dose currently used in RA0043 is proposed to provide a pragmatic dosing regimen that will yield a closer match to the adult plasma concentration range achieved in adults with the approved label for RA (CZP 400mg at Weeks 0, 2, and 4 followed by CZP 200mg Q2W thereafter).
Amendment 4.1	01 Aug 2013	Amendment 4 adapted for Russia as per Amendment 2.1.
Amendment 5	20 Jan 2014	The primary purpose of this substantial amendment is to reopen enrollment under the new reduced CZP dose regimen and to update the statistical analysis to account for the changes in the CZP dose regimen.
Amendment 5.1	20 Jan 2014	Amendment 5 adapted for Russia as per Amendment 2.1.
Amendment 5.2	23 Feb 2015	The primary purpose of this non-substantial amendment is to lift the enrollment cap per site in Russia to allow further enrollment in the weight group of 15 to <20kg for sites that have enrolled the maximum number of 12 study participants.
Amendment 6	17 Sep 2015	The primary purpose of this administrative amendment is to update the packaging and labeling sections of the protocol to account for a new presentation of the prefilled syringe (PFS).
Amendment 6.1	17 Sep 2015	Amendment 6 adapted for Russia as per Amendment 2.1.
Amendment 7	22 Sep 2016	The primary purpose of this substantial amendment is to update the protocol in accordance with current UCB TB detection procedures, including the introduction of yearly TB testing and the extension of the prophylactic TB treatment duration from 4 to 8 weeks. Furthermore, it has been clarified that long-term efficacy data from study participants who withdraw from the study after Week 56 or initiate any rescue medication use after Week 56 will be analyzed "as observed" and will no longer be imputed as nonresponse or missing.

Confidential Page 12 of 252

**Table 2–1:** Protocol, Amendments, Dates and Rationales

Amendment 7.1	22 Sep 2016	Amendment 7 adapted for Russia as per Amendment 2.1.

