## 4.2 Handling of dropouts or missing data

For all binary efficacy endpoints assessing response (PedACR30, PedACR50, PedACR70, PedACR90, CID, CRM), a study participant having missing data for the time point assessed will be conservatively counted as a non-remitter or non-responder. This will be done whether the data is missing, the study participant discontinued the study prior to the time point assessed, or the data is considered missing due to use of prohibited or rescue medication.

For all non-missed visits, if any of the PedACR core set measures are missing then those scores will be considered as not having met the criteria for improvement in the PedACR30, PedACR50, PedACR50, PedACR50 and PedACR90 response analyses. PedACR30, PedACR50, PedACR50, and PedACR90 responses will be derived if a single core set measure is missing. However, if 2 or more core set measures are missing, the corresponding PedACR30, PedACR50, PedACR50 and PedACR90 responses will in general be treated as missing.

Derived binary efficacy endpoints at visits affected by the use of rescue medications, or prohibited medications, will be treated as non-response. See Section 6.7 for a list of medications which would result in all efficacy data at only the next scheduled visit (and not all subsequent visits) being treated as missing/non-response. Any joint receiving intra-articular corticosteroids will be treated as missing with respect to assessments of that joint for 3 months (91 days).

For continuous efficacy endpoints, missing assessments will not be imputed.

For the non-responder imputation (NRI) calculations for binary efficacy outcomes,

- the study participants who discontinued up to and including Week 56, NRI will be imputed up to Week 56,
- the study participants who discontinued after Week 56, no imputation will be performed after the last visit,
- for study participants who take rescue and prohibited medications (see Section 6.6),
  - for visits up to and including Week 56, the outcomes are imputed as NRI up to Week
     56
  - for visits after Week 56, the outcomes are imputed as NRI if medication initiation is before or on Week 56
- for the initiation of rescue, short-acting or prohibited medications after Week 56, then the NRI imputation is not applied.

No further imputations of any other missing data are planned (eg, efficacy data missing at random).

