## 6.5 Prohibited medications

The following medications are prohibited at any time during the study:

- Nonbiologic DMARDs (other than MTX) and biologic DMARDs (eg, anakinra, rilonacept, etanercept, adalimumab, infliximab, golimumab, rituximab, abatacept, tocilizumab, CZP other than study medication).
- Any experimental (biological or non-biological) therapy (within or outside a clinical study).
  Live and live attenuated vaccineties.
  - Live and live attenuated vaccinations including, but not limited to, oral polio, chicken pox (varicella), measles-mumps-rubella (MMR), nasal influenza, and rotavirus. No data are available on the response to live vaccinations or the secondary transmission of infection by live vaccines in study participants receiving CZP.

All efficacy data collected at any assessments after the use of prohibited medications that could impact efficacy will be treated as non-response for binary endpoints in all analyses The +1 day rule was applied to the first usage date when considering its impact on efficacy endpoints. Therefore, only efficacy data with dates after the first usage date of the prohibited medication were impacted (using the non-responder imputation (NRI) method).

All summaries of prohibited medications will be provided for the CC ?

Dose, the Original CZP Dose and the Any CZP ?

listed.

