## 6.7 Short-acting medications

Use of the following medications, which are not rescue medications, only results in efficacy data at the next scheduled visit being treated as missing/non-response:

- Higher than Baseline dose of nonsteroidal anti-inflammatory drugs (NSAIDs) and cyclooxygenase-2 (COX-2) inhibitors, including as needed (PRN) use within 72 hours prior to scheduled study visit (Note: No intake at baseline is considered equivalent to a baseline dose of 0).
  - Higher than Baseline dose of analgesics or opioids including PRN use within 48 hours prior to scheduled study visit (Note: No intake at baseline is considered equivalent to a baseline dose of 0).
- Any increase in dose of oral corticosteroids within 7 days prior to scheduled study visit (Note: The increase has to be higher than baseline).

Confidential

All medication data resulting in efficacy data being treated as missing/non-response will be flagged in the concomitant medication listing.

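### Sections 4.2 and 6.5 contradict each other on how to count binary response after a prohibited, efficacy-relevant medication is started after Week 56

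*SAP*

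**What the plan says.** Section 4.2 first gives an unlimited rule: "Derived binary efficacy endpoints at visits affected by the use of rescue medications, or prohibited medications, will be treated as non-response". It then lists non-responder imputation (NRI) rules built around Week 56. Where rescue or prohibited medication starts on or before Week 56, outcomes are imputed as non-response both up to and after Week 56. The last rule covers later starts: "for the initiation of rescue, short-acting or prohibited medications after Week 56, then the NRI imputation is not applied".

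Section 6.5 opens its list with "The following medications are prohibited at any time during the study", and the first entry is "Nonbiologic DMARDs (other than MTX) and biologic DMARDs". Its analysis rule is that efficacy data at any assessment "after the use of prohibited medications that could impact efficacy will be treated as non-response for binary endpoints in all analyses". No Week 56 limit appears there.

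Section 6.7 says that use of short-acting medication "only results in efficacy data at the next scheduled visit being treated as missing/non-response". It also has no Week 56 limit.

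The only stated reason in this SAP for analysing data after Week 56 as observed is the Protocol Amendment 7 entry in Table 2-1 (Section 2). It covers participants who withdraw after Week 56 or who "initiate any rescue medication use after Week 56 will be analyzed" as observed. It names neither prohibited nor short-acting medication.

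**The concern.** A programmer following 4.2 keeps the observed response of a participant who starts another biologic DMARD after Week 56. A programmer following 6.5 sets that visit to non-response. Both can claim to have followed the plan.

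The affected displays are the long-term ones. Section 10.3.1 summarises PedACR response at every visit except the Final Visit, and Sections 10.3.9 and 10.3.10 do the same for derived inactive disease and derived remission. Table 2-1 records that all ongoing participants had completed at least Week 180 when Amendment 8 was implemented, and Section 9.1.1 tabulates exposure up to 96 months or more. Much of the long-term efficacy display therefore lies beyond Week 56. Under 4.2, a response obtained on another DMARD would be tabulated as a response on CZP. If the conflict is left open, the choice could be made after the data are seen.

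**Working it through.** There is no sample size, power or error rate to reproduce, so the check is mainly a comparison of the rules in the current text.

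| Medication class | Start on or before Week 56 | Start after Week 56 |
|---|---|---|
| Rescue (6.6) | Non-response under 4.2 | 4.2: NRI not applied. The lists in 6.6 stop at Week 16 or Week 56, so they agree. |
| Prohibited, efficacy-relevant (6.5) | Non-response under both 4.2 and 6.5 | 4.2 last rule: NRI not applied. 6.5: non-response in every analysis. 4.2 general sentence: non-response. **Contradiction.** |
| Short-acting (6.7) | Next scheduled visit missing/non-response | 4.2: NRI not applied. 6.7: no time limit stated. Not aligned, but can be read together. |

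**One record, two results.** Suppose a participant starts a prohibited biologic at Week 80 and meets PedACR30 at Week 88. Section 4.2 makes Week 88 a response; Section 6.5 makes it a non-response.

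**Scale.** Let n be the number in the denominator at a visit, the same under both rules. Let k be the number of observed responders there who started such a drug after Week 56.

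- Shift in the rate = k/n. Users who are not observed responders do not move it.
- Section 3.1 suppresses efficacy visits with 19 or fewer non-missing participants in Any CZP Dose, so the smallest displayed Any CZP visit has n = 20.
- With n = 20 and an assumed 15 responders, 15/20 = 75.0% (exact 95% CI 50.9 to 91.3). With k = 1, 14/20 = 70.0% (45.7 to 88.1). The shift is 1/20 = 5.0 points.
- With an assumed n = 100 and 75 responders, k = 1 gives 74/100 = 74.0%. The shift is 1/100 = 1.0 point.

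The 20-participant threshold applies to Any CZP Dose only. Dose and weight groups at the same visit can be smaller, so one participant can move those rates by more than 5 points. The SAP gives no value for k.

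**Cross-reference.** The 4.2 rule for rescue and prohibited medications points only to Section 6.6. Prohibited medications are defined in 6.5.

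**The case against.** The best reply is that the intent can be guessed. Section 4.2 is the dedicated missing-data section, and its last rule is the only text that addresses a start after Week 56. It names all three medication classes. The log for SAP Amendment 5 (Section 13.5) shows that the Week 56 rules in 4.2 replaced wording close to what 6.5 still says, and that the rescue lists were limited to Week 56 in the same amendment. The 6.5 sentence may simply have been left behind. That is plausible but does not settle the matter: no precedence is stated, 6.5 claims to apply to every analysis, and 4.2 keeps its own unlimited sentence.

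For short-acting medication the reply largely succeeds. Section 6.7 fixes which visit is affected and does not claim to govern every analysis. Section 4.2 refers to 6.7 and then adds a Week 56 limit that names short-acting use. A general rule with a stated limit is a natural reading, so this calls for alignment rather than resolution of opposite rules.

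Three stronger readings are tempting and are not supported:

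- A reader might infer that the long-term rates are off by many points. At n = 100, a shift of 5 points needs five observed responders on such drugs, and the SAP gives no count. Whether use of such a drug leads to withdrawal is not shown. Participants who withdraw after Week 56 add no later visits, because 4.2 imputes nothing after the last visit.
- A reader might infer from the Amendment 7 entry that the protocol restricts the as-observed rule to rescue and withdrawal. The entry is a short rationale in a table and the protocol is not at hand. Its silence shows only that this SAP gives no reason for the wider rule.
- A reader might infer that the main results are at risk. The primary variables are PK, immunogenicity and safety, and the secondary efficacy variable is PedACR at Week 16.

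Affected participants would also be traceable. Prohibited use is summarised and listed, and efficacy is listed by participant. The tabulated rate would still depend on the rule chosen.

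**Conclusion.** The contradiction between 4.2 and 6.5 is real and stands in the current text. It concerns the binary efficacy variables after Week 56, in participants who start a prohibited, efficacy-relevant medication after Week 56. Section 6.5 is limited to drugs that could affect efficacy, so live vaccines may fall outside it; biologic DMARDs plainly fall within it. The mismatch with 6.7 is a lesser matter of alignment.

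The size is 1/n per affected observed responder, assuming the denominator is the same under both rules. The number affected is unknown. No hypothesis is tested, so no error rate is at stake; what is at stake is which long-term rates are reported. This is a should-fix point.

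**What to change.** Before the final analysis, reconcile Sections 4.2, 6.5 and 6.7 so that each medication class has one stated analysis rule after Week 56.

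- **Prohibited, efficacy-relevant medication.** Non-response, as 6.5 has it, avoids counting a response on another DMARD as a CZP response. It also fits the only stated rationale in this SAP for the as-observed rule, which names withdrawal and rescue. In that case, remove prohibited medication from the last NRI rule in 4.2. If the 4.2 rule is kept, amend 6.5 and the general sentence in 4.2 to say so, and show the non-response result alongside. Either choice removes the contradiction.
- **Short-acting medication.** State in 6.7 whether the next-visit rule stops at Week 56, in agreement with 4.2.
- **Cross-reference.** Point the 4.2 rule on prohibited medications to Section 6.5.

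This changes how data are counted, not how participants are managed. The cost is a few sentences and a flag in the efficacy datasets, plus one extra row if the alternative result is shown. Under the non-response rule, some long-term rates may be slightly lower.

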### Incomplete date for the last administration of study medication 4.2.2

No imputation should be performed for missing study medication start dates. This field on the CRF should not be partial or missing.

For partial or missing date of last dose of study medication, the following imputation rules will be applied for the purpose of calculating overall exposure:

If the day is missing (but month and year available), impute the last dose date as the minimum of the last day of the month or the date of last contact reported on the Study Termination CRF; if day and month are both missing (only year available), impute the last dose date as the minimum of the last day of the year or the date of last contact on the Study Termination CRF.

If a study participant died and has a partial or missing last administration date, the date is to set to the date of death. If there is a partial date of last dose and the month/year are prior to the month and year of the date of death, follow partial date imputation rules.

If the last dose date is completely missing and no information could be obtained from data cleaning exercises, the last dose date should be imputed as the date of last contact according to the Study Termination CRF. A review of the data for study participants with completely missing last dose dates should be performed to ensure that the imputation does not result in an unrealistic value for duration of exposure.

Imputed date of last dose dates should only be used for calculation of the duration of exposure. The date as recorded on the CRF should be presented in study participant data listings (no imputed dates should be included in study participant data listings).

## 4.2.3 Handling of questionnaire data

When relevant, the following rules will apply for analysis of (1) out of range and (2) ambiguous answers (i.e. invalid or unable to interpret answers) to questionnaires completed by study participants or parents/caregivers:

1. In case of an out-of-range answer (i.e., an answer that does not correspond to any possible response proposed in the questionnaire, e. g. "?", "I don't know" or any value superior or inferior to the ones specified in the response options): the answer will be scored "missing".

However, in case the study participant or parent/caregiver selected one of the proposed responses but added a comment (for instance "6 +++" or "5?"), the response (i.e., "6" or "5") will be retained for scoring but not the comment (i.e., "+++" or "?").

In the same way, if the study participant or parent/caregiver selected one of the proposed responses but added a value superior or inferior to the ones specified in the response options (for instance "4/5" or "-1/2" on a 5-point scale ranging from 0 to 4), the response corresponding to the possible responses options (i.e., "4" or "2") will be retained for scoring but not the values superior of inferior to the responses options (i.e., "5" or "-1").

- 2. In case of an ambiguous answer (i.e., multiple responses to a question allowing only a single response, a response marked between two allowed responses):
  - a) Multiple responses to a question allowing only a single response:
    - i) If half or more responses are marked (i.e., 4 responses marked on a seven-point scale, 3 responses marked on a 5-point scale, 2 responses to a Yes/No item...): the answer will be scored "missing".
    - ii) If less than half of the responses are marked:
      - (1) if the responses are NOT adjacent to each other: the answer will be scored "missing",
      - (2) if the responses are adjacent to each other ("2/3" or "2/3/4", for instance), the more severe score will be retained.
  - b) If a response is marked between two allowed responses (for instance, the study participant marked his/her response between 2 and 3 on a 4-point scale allowing only responses 1, 2, 3 and 4): the nearest more severe score will be retained.

## 4.2.4 Missing adverse event intensity

If the intensity of an AE is missing, then it will be counted as severe for analysis purposes.

## 4.2.5 Missing adverse event relationship to study medication

If the AE relationship to study medication is missing, then it will be counted as related for analysis purposes.

## 4.3 Interim analyses and data monitoring

A futility analysis of the PedACR30 response rate was performed after all active study participants who enrolled prior to Protocol Amendment 9 had completed the Week 16 (Visit 8) assessments. If less than 50% of the study population enrolled on the Reduced CZP Dose (Protocol Amendment 5) achieved a PedACR30 response at Week 16, the study was to be discontinued. The futility analysis confirmed that ≥50% of the study population enrolled on the Reduced CZP Dose achieved a PedACR30 response at Week 16. Given the descriptive nature of the data presentations, there were no statistical implications of this interim analysis. A further futility analysis will not be performed using the additional study participants that will be enrolled on the Original CZP Dose following the implementation of Protocol Amendment 9.

In addition to the futility analysis, several interim analyses were planned, including interim analyses of PK data, and full interim analyses of PK, immunogenicity, safety, and efficacy endpoints, as described below.

## Interim analyses of PK data

Per original protocol, if the pediatric plasma concentrations demonstrate that the geometric mean and median concentrations are below the adult 5th percentile or above the 95th percentile, the PK data will be used to re-evaluate the weight-based dose adjustment algorithm for pediatric study participants. Interim CZP plasma concentration data available at the time of Protocol Amendment 3 indicated that no change to the dosing algorithm was required. The protocol stated that if future interim analyses, which may include PopPK, indicate that plasma concentrations of pcJIA study participants are outside of the exposure range observed in previous adult RA studies, a revised pediatric dose algorithm will be derived. Any change in doses will require a protocol amendment prior to implementation.

An interim analysis of PK data conducted following Protocol Amendment 3 compared CZP plasma concentration data from RA0043 with CZP plasma concentrations observed previously in adult study participants with RA. Interim analysis of CZP plasma concentrations was started when 6 study participants in 1 of the age groups completed Week 12 (Visit 7). Comparisons were made between the Week 12 geometric mean and median values for the pediatric and adult study participants, as well as between the individual pediatric data and the adult 5th and 95th percentile and minimum and maximum observed values.

Based on results of this interim PopPK analysis, the doses were changed with Protocol Amendments 4 and 5, and the doses to be administered were reduced by 50% for all weight groups. This change was intended to achieve plasma concentrations similar to the effective concentrations observed in the previous study in adult study participants with RA (study C87050).

Interim analyses of PK, immunogenicity, safety, and efficacy endpoints

An interim analysis of PK, immunogenicity, safety, and efficacy endpoints was performed after all active study participants that were enrolled and treated prior to implementation of

At the time of Protocol Amendment 9, a new assay had been developed and was used to analyze samples from the 30 new study participants enrolled on the original dose as well as any old samples with sufficient volume remaining. An interim analysis. including the study participants, for all PK, immunogenicity, safety, and after all active study participants, including the Under the Under the sum of the sum of the same that the sum of the same that t the Updated Week 24 Interim analysis that was used in support of the re-submission of BLA 125160-275.

All statistical tables, listings and figures comprising this SAP will be produced for all future interim and final analyses. Interim data from RA0043 may be summarized to support regulatory submissions, regular safety signal detection monitoring, publications and annual reports to regulatory agencies. For any interim data summary, all available data as of the time of the clinical cut-off date will be included. Study participants ongoing at the time of an interim data summary will be assumed to be treated (ie exposed) up to and including the date of the clinical data cut-off; efficacy data will not be imputed for the closest visit to the clinical snapshot date if the visit is not currently in the clinical database; composite variables will not be calculated if one or more components are unavailable for the visit closest to the clinical snapshot date.

A Data and Safety Monitoring Board (DSMB) will periodically review all emerging safety data. The DSMB consists of 3 external pediatric experts and an external pharmacometrician and is independent of the Sponsor and Investigators. The DSMB members will be informed by the Drug Safety representative (or designee) of all serious adverse events (SAEs) at the time of expedited reporting and will review periodically all emerging safety data (eg, SAEs, AEs, safety laboratory data). Based on the safety data, the DSMB can recommend modifying/stopping the study.

Further interim analyses may be performed at the Sponsor's discretion as required.

